## Additional Responder Definitions

### Eye Responder

#### Criteria 1

Responder will be defined as an eye that loses less than or equal to +0.2 LogMAR. Early discontinuations will be considered as non-responder for both eyes.

#### Criteria 2

Responder will be defined as an eye that loses less than or equal to +0.3 LogMAR. Early discontinuations will be considered as non-responder for both eyes.

#### Criteria 3

Responder will be defined by an improvement of at least -0.2 LogMAR compared to baseline. Early discontinuations will be considered as non-responder for both eyes.

#### Criteria 4

Responder will be defined by an improvement of at least -0.3 LogMAR compared to baseline. Early discontinuations will be considered as non-responder for both eyes.

#### Criteria 5

Responder will be defined by an improvement of at least -0.4 LogMAR compared to baseline. Early discontinuations will be considered as non-responder for both eyes.

#### Criteria 6

Responder will be defined by an improvement of at least -0.5 LogMAR compared to baseline. Early discontinuations will be considered as non-responder for both eyes.

#### Criteria 7

Responder will be defined as an eye that has 20/200 or better visual acuity. Early discontinuations will be considered as non-responder for both eyes.

Criteria 8

Responder will be defined as an eye that has better than 20/200 visual acuity. Early discontinuations will be considered as non-responder for both eyes.

Criteria 9

Responder will be defined as an eye whose improvement of HVF Parameters (Mean deviation or Foveal Sensitivity) from baseline is at least 1 time the coefficient of repeatability. Early discontinuations will be considered as non-responders.

Criteria 10

Responder will be defined by an improvement of at least +0.2 LogCS compared to baseline. Early discontinuations will be considered as non-responder for both eyes.

Criteria 11

Responder will be defined by an improvement of at least +0.3 LogCS compared to baseline. Early discontinuations will be considered as non-responder for both eyes.

Criteria 12

Responder will be defined for the eyes which were On-Chart eyes at baseline and which have an improvement of at least -0.2 LogMAR or which were Off Chart at baseline but became On Chart with at least 5 ETDRS letters at a particular visit

Criteria 13

Responder will be defined for the eyes which were On-Chart eyes at baseline and which have an improvement of at least -0.3 LogMAR or which were Off Chart at baseline but became On Chart with at least 5 ETDRS letters at a particular visit

Criteria 14

Responder eye will be defined not legally blind both at baseline and Week 48/72/96 (LogMAR < 1.0 or Snellen > 20/200)

Criteria 15

Responder will be defined by an improvement of at least -0.2 LogMAR compared to post-treatment Nadir. Early discontinuations will be considered as non-responder for both eyes.

Criteria 16

Responders will be defined by an improvement of at least -0.3 LogMAR compared to post-treatment Nadir. Early discontinuations will be considered as non-responder for both eyes.

## Subject Responder

### Criteria 1

Responder will be defined as a subject whose change of LogMAR from baseline in the treated eye is at least -0.2 better than the change from baseline of LogMAR in Sham eye. Early discontinuations will be considered as non-responders.

### Criteria 2

Responder will be defined as a subject whose change of LogMAR from baseline in the treated eye is at least -0.3 better than the change from baseline of LogMAR in Sham eye. Early discontinuations will be considered as non-responders.

### Criteria 3

Responder will be defined as a subject whose change of LogCS from baseline in the treated eye is at least +0.2 LogCS better than the change from baseline of LogCS in Sham eye. Early discontinuations (prior to W48 for the primary endpoint) will be considered as non-responders.

### Criteria 4

Responder will be defined as a subject whose change of LogCS from baseline in the treated eye is at least +0.3 LogCS better than the change from baseline of LogCS in Sham eye. Early discontinuations (prior to W48 for the primary endpoint) will be considered as non-responders.

## Vision Loss Duration at Screening

Vision loss duration in days will be based on the difference between the date of onset of vision loss per eye and Screening date.

## ETDRS/LogMAR and on-chart and off-chart:

- I. 1 ETDRS line = 5 letters
- II. 1 ETDRS line = 0.1 LogMAR
- III. 0.1 LogMAR = 5 ETDRS letters
- IV. 15 ETDRS letters = 0.3 LogMAR
- V. A less positive/more negative LogMAR is an improvement of vision
- VI. An increase in the number of ETDRS letters read is an improvement of vision

On-Chart subjects: defined as being able to read at least 3 ETDRS letters on a single line on the ETDRS chart at either 4 or 1 meters

- a. Have an obtainable Snellen equivalent obtained directly from ETDRS chart
- b. Each Snellen equivalent is assigned a LogMAR value

Off-chart Subjects: defined as a subject who cannot read at least 3 ETDRS letters on a single line of the ETDRS chart at either 4 or 1 meters and thus have no Snellen equivalent obtainable from ETDRS chart

- c. These subjects are categorized as able to either count fingers (CF), detect hand motion (HM), detect light perception (LP) or are no-light perception (NLP)
- d. For those categorized as either CF or HM a method for deriving LogMAR visual acuity is pre-specified
- e. The distance at which CF/HM vision was obtained is recorded per the standard operating procedure
- f. Study database derives the LogMAR based on this distance and the finger/hand dimensions of the examiner, per pre-specified method.

Treatment-Emergent Adverse Events (TEAE)

Treatment-emergent adverse events (TEAEs) are defined as AEs that started after study treatment administration at Visit 3 or that represent an exacerbation of a condition that is present at baseline after treatment administration. Worsening of visual acuity determined by the investigator to be due to progression of LHON will not be considered as an AE. Any AE with an unknown start date will be considered treatment-emergent if the event does not stop prior to study treatment administration. AEs with partial dates are described in [Section 5.7.2](#).

Prior and Concomitant Treatment

Prior treatments will be defined as any treatments with start date and time prior to the study treatment administration date and time.

Concomitant treatments will be defined as any treatments ongoing at the start of study treatment administration or with a start date and time on or after the study treatment administration date and time. Treatments with partial dates will be dealt similarly as AEs with partial dates described in [Section 5.7.2](#). If the start time is missing, then treatments will be assigned ‘concomitant’ based on start date of treatments only if it is on or after the treatment administration date.

[Redacted]

[Redacted]

[Redacted]

### Ocular Inflammation Score

The Ocular Inflammation Score (OIS) was defined as the global score calculated by adding the grades obtained for Anterior Chamber cell + Anterior Chamber haze + Vitreous Cell + Vitreous Haze

## **5.7 HANDLING OF MISSING DATA AND/OR INVALID DATA AND OUTLIERS**

### **5.7.1 Efficacy**

If a subject's visual acuity is light perception and no LogMAR can be assigned, then a LogMAR value of 4 will be assigned. If a subject's visual acuity is no light perception, then a LogMAR value of 4.5 will be assigned.

In case of missing data at Week 48, the following rules will be applied in the primary imputation method:

Rule 1: If the LogMAR is available at the previous and the following visits then the imputed value at Week 48 will be a linear interpolation of LogMAR.

Rule 2: If there is no following visit due to drop out then the relative change ( $RC_i$ ) from visit  $V_i$  to visit  $V_{i+1}$  will be calculated at each visit from the baseline to the visit preceding Week 48 in the group treated with a sham. The last available visit ( $V_i$ ) with data ( $X_i$ ) will be used as the starting time point. The imputed score at  $V_{i+1}$  for each eye will be equal to  $X_{i+1} = X_i + X_i * RC_i$ . The imputed score at the next missing visit  $V_{i+2}$  will be equal to  $X_{i+2} = X_{i+1} + X_{i+1} * RC_{i+1}$ , and so on up to Week 48 visit. The  $RC_i$  will be the same for the treated and sham eyes.

With the primary method of imputation, the between eye difference at Week 48 will be proportional to the between eye difference at the time of withdrawal because the same RCi coefficients are used for both eyes.

The secondary imputation method leading to an additional sensitivity analysis will apply the same Rule 1 but Rule 2 will be based on the evolution of the difference between treated and sham eye. RCi is then the relative change from visit i to visit i+1 of the difference between treated and sham eye in all subjects attending visit i and i + 1.

Other:

When a test result score/value for the Pelli-Robson Contrast test, or the Farnsworth-Munsell 100 Hue Color test is missing at any visit, for the reason that the subject was unable to perform because the vision was too poor or unable to perform within the constraints of time limitation pre-defined in the Standard Operating Procedure (for the Farnsworth-Munsell 100 Hue Color test), the following convention will be utilized: the worst possible score for the given test will be utilized as the value for that visit.

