5.2 Selection for the Study

5.2.1 Selection Criteria

Subjects must meet all the following criteria at the Screening Visit (Visit 1) in order to be included into the study.

- 1. Age 15 years or older.
- 2. Onset of vision loss based on medically documented history or subject testimony, in at least one eye for ≤ 180 days in duration and if both eyes are affected the duration of vision loss in both eyes must be ≤ 180 days in duration.
- 3. Each eye of the subject maintaining visual ability to allow at least for counting of the examiner's fingers at any distance.
- 4. Female subjects (if of childbearing potential) must agree to use effective methods of birth control up to 6 months after IVT injection and male subjects must agree to use condoms for up to 6 months after IVT injection.
- 5. Ability to obtain adequate pupillary dilation to permit thorough ocular examination and testing.
- 6. Signed written informed consent.

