6.2 Premature Discontinuation

Subjects who discontinue participation in the study prematurely (i.e. prior to Visit 12) will complete an end-of-study visit including all procedures listed for Visit 12.

A subject will be withdrawn from the study under any of the following circumstances:

- Subject's request at any time for any reason.
- Physician's determination that subject's further participation in the protocol is not in the subject's best interest.
- The Sponsor's decision.
- Health Authorities' decision.

For any discontinuation, the Investigator will obtain all the required details and document the date of and the reason for the discontinuation in the case report form (CRF). If possible, Week 48 ETDRS visual acuity should be obtained.

If the reason for withdrawing from the study is an AE, the specific event will be recorded in the CRF.

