12.7 Handling of Missing Data

In case of missing data at Week 48, the following rules will be applied in the first imputation method:

Rule 1: If the LogMAR is available at the previous and the following visits then the imputed value at Week 48 will be a linear interpolation of LogMAR.

Rule 2: If there is no following visit due to drop out then the relative change (RC_i) from visit V_i to visit V_{i+1} will be calculated at each visit from the baseline to the visit preceding Week 48 in the group treated with a sham. The last available visit (V_i) with data (X_i) will be used as the starting time point. The imputed score at V_{i+1} for each eye will be equal to $X_{i+1} = X_i * RC_i$. The imputed score at the next missing visit V_{i+2} will be equal to $X_{i+2} = X_{i+1}*RC_{i+1}$, and so on up to Week 48 visit. The RC_i will be the same for the treated and sham eyes.

With the first method of imputation the between eye difference at Week 48 will be proportional to the between eye difference at the time of withdrawal because the same RC_i coefficients are used for both eyes.

The second imputation method leading to an additional sensitivity analysis will apply the same Rule 1 but Rule 2 will be based on the evolution of the difference between treated and sham eye. RC_i is then the relative change from visit i to visit i+1 of the difference between treated and sham eye in all subjects attending visit i and i + 1. The sensitivity analysis will be a one sample t-test performed on the difference between treated and sham eyes at Week 48. This method assumes that the evolution of drop-out is similar in terms of between eye differences to that of subjects who were followed-up.

The third imputation method will apply the same Rule 1 but for Rule 2 the last available data will be carried forward for the sham eye and the worst available value (either sham or treated eye) will be carried forward for the treated eye. This should be the most conservative imputation method.

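### Primary imputation Rule 2 multiplies LogMAR by a sham-trend factor, and the secondary method gives no per-eye value: wrong as written, minor in size

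*SAP*

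**What the plan says.** **Primary method.** SAP 5.7.1, Rule 2, applies where Week 48 is missing: "If there is no following visit due to drop out then the relative change" is taken from the sham group and applied to both eyes. The SAP update is X + X·RC; Protocol 12.7 prints X·RC. The SAP states the consequence, that "the between eye difference at Week 48 will be proportional to the between eye difference at the time of withdrawal". Protocol 12.7 says the same: "With the first method of imputation the between eye difference at Week 48 will be proportional".

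**Scale.** SAP 5.6 notes that "A less positive/more negative LogMAR is an improvement of vision" and that "0.1 LogMAR = 5 ETDRS letters". SAP 5.7.1 assigns 4 to light perception and 4.5 to no light perception.

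**Entry.** Protocol 5.2.1 criterion 2 requires vision loss in at least one eye, "and if both eyes are affected the duration of vision loss in both eyes must be" within 180 days. One eye may therefore be unaffected. Criterion 3 ("Each eye of the subject maintaining visual ability to allow at least for counting of" the examiner's fingers) limits only how poor the vision may be. No criterion limits how good it may be.

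**Secondary method.** RC is the relative change of the treated-minus-sham difference. Protocol 12.7 pairs this with a one-sample t-test on the Week 48 difference, a sentence that SAP 5.7.1 does not carry over. SAP 9.5.1 instead reruns the primary model with this method as items 3 and 16 of both sensitivity lists: the EMA mixed model, with a baseline value for each eye, and the FDA ANCOVA on best-seeing eyes.

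**The concern.** A multiplicative update makes sense on a scale where zero means none of the quantity. LogMAR is a logarithm: its zero is a reference acuity, and values on either side of it are ordinary scores. Multiplying by a common factor makes the imputed movement depend on how far an eye happens to lie from that reference. The endpoint is an additive change from baseline, so the imputation and the endpoint treat the scale differently.

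Rule 2 values enter the primary analysis for both agencies. At stake is whether a dropout's imputed difference in change reflects what was observed up to withdrawal or is partly a product of unequal starting acuity. The secondary method is the listed check on this handling of missing data, and it does not supply the values its models need.

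**Working it through.** **Inputs.** From the documents: 36 subjects, an SD of 0.594 for the between-eye difference in change (SAP 3.3, from the Phase I/II study), and 50 letters per LogMAR unit. The documents give no dropout rate and no sham trend, so the total RC over the remaining visits is assumed, from −0.10 to 0.25.

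**Plan's own figure.** The plan gives no numerical result for the imputation rule. The two figures borrowed from SAP 3.3 reproduce: 0.3/0.594 = 0.505, and a two-sided paired t-test with n = 36 then has 83.8% power, against the stated 84%.

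**Step 1, single eyes.** The imputed change is X·RC, converted at 50 letters per unit:

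| Last LogMAR | RC −0.10 | RC 0.05 | RC 0.10 | RC 0.25 |
|---|---|---|---|---|
| 1.2 | 6 letters gained | 3 lost | 6 lost | 15 lost |
| 0 | none | none | none | none |
| −0.1 | 0.5 lost | 0.25 gained | 0.5 gained | 1.25 gained |

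The eye at 0 never moves. The eye below 0 moves against the sham trend in every column.

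**Step 2, the gap.** A between-eye gap g becomes g(1 + RC). A gap of 0.3 becomes 0.27, 0.315, 0.33 and 0.375 across the same four values of RC.

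**Step 3, unequal but unchanged eyes.** Take eyes at 1.2 and 0 at both baseline and last visit. The difference in change to date is 0. Rule 2 imputes (1.2 − 0)·RC, which is 0.06, 0.12 and 0.30 in size for RC 0.05, 0.10 and 0.25. With a worsening sham trend it favours GS010 if GS010 was given to the eye at 0, and counts against it if given to the eye at 1.2.

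**Step 4, effect on the EMA estimate.** One such dropout at RC 0.25 shifts the unadjusted mean difference by 0.30/36 = 0.0083. With SE = 0.594/√36 = 0.099, that is 0.0083/0.099, or about 8% of one SE.

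**Step 5, secondary method.** Suppose the last values are 0.8 (GS010) and 1.1 (sham), a difference of −0.30, and the difference RC is assumed to be 0.5. The imputed difference is −0.30 × 1.5 = −0.45. The GS010/sham pairs 0.65/1.10, 0.80/1.25 and 0.98/1.43 all satisfy it. No unique value exists for either eye, yet both models take one value per eye.

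**Step 6, additive alternative.** Adding the same increment c to both eyes in Step 3 gives 1.2 + c and 0 + c. The gap stays 1.2 and the difference in change stays c − c = 0, wherever the zero of the scale lies.

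**The case against.** Both documents state the proportionality openly, so it is a declared property of the method. Few subjects should be affected. Rule 2 applies only to dropouts before Week 48 with no later visit, and Protocol 6.2 asks for an end-of-study visit and adds "If possible, Week 48 ETDRS visual acuity should be obtained". Observed values, Rule 1 interpolations and the per-protocol analysis are untouched. The wrong-way movement at −0.1 is at most 1.25 letters in the range examined. Allocation of GS010 is balanced between better- and worse-seeing eyes, so errors of the Step 3 kind tend to cancel in the EMA mean. Both primary models also adjust for baseline LogMAR. The additive rule is itself a single imputation, not shown to be nearer the truth.

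All of this stands as an argument about size. It does not rescue the rule: declaring that the gap will be proportional does not give LogMAR a meaningful zero.

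Three stronger readings are tempting, and the documents do not support them.

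- A reader might divide the 0.30 by an FDA arm of about 18 eyes. That is not valid. The FDA model uses only best-seeing eyes, and in Step 3 the whole 0.30 arises in the worst-seeing eye; the best-seeing eye stays at 0. No FDA shift can be read from a between-eye gap.
- A reader might infer a systematic bias towards GS010. The sign depends on which eye was treated and on the direction of the sham trend, so no direction can be claimed.
- A reader might see the protocol and SAP formulas as contradictory. They are the same rule if RC is a ratio in one and a fractional change in the other, and Protocol 12.1 leaves detailed data-handling rules to the SAP. The missing equation and averaging rule are mainly missing detail.

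**Conclusion.** Rule 2 is wrong as written on the LogMAR scale, and the consequence is minor. It freezes an eye at 0, moves an eye below 0 against the sham trend, and rescales the gap at withdrawal by that trend. For the illustrated dropout, the shift in the EMA mean difference is about 0.008 LogMAR. This rests on an assumed RC of 0.25, eyes at 1.2 and 0, and no baseline adjustment; the adjusted shift was not calculated. The comparison with an SE of 0.099 also assumes that the Phase I/II SD applies to this trial.

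The gap in the secondary method needs no numerical assumption. Items 3 and 16 cannot be fitted as written, for either agency's model, once any subject needs that method. If no subject does, the gap has no effect.

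**What to change.** Make these changes before the randomization code is broken, since Protocol Appendix V allows no SAP amendment afterwards.

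1. **Primary Rule 2, both documents.** Set X(i+1) = X(i) + the mean LogMAR change from visit i to visit i+1 over all sham eyes observed at both visits, best- and worst-seeing together. Use the same increment for both eyes and limit imputed values to 4.5.
2. **Proportionality sentence, both documents.** Replace it with a statement that the between-eye difference at withdrawal is carried forward unchanged unless the 4.5 limit applies.
3. **Secondary method.** Impute each eye with the mean additive change of all eyes in its own treatment arm (GS010 or sham) observed at both visits, under the same limit. Every eye then has a value, and both the EMA and FDA models can be fitted.

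The cost is a short revision of SAP 5.7.1 and a protocol amendment to 12.7 under Protocol 15, with no new data. The downside is that the additive rule is not shown to be closer to the truth for an unaffected eye about to become involved; either rule can be far off there.

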#### Primary Analysis for EMA

The null and alternative hypotheses for the primary endpoint are defined below

$$H_0: \mu_{\text{All-GS010}} = \mu_{\text{All-Sham}}$$

$$H_1: \mu_{\text{All-GS010}} \neq \mu_{\text{All-Sham}}$$

Where  $\mu$  presents the mean change from baseline to Week 48 in LogMAR. “All” represents all eyes treated with GS010 or Sham

The primary analysis will be performed on the ITT population. The change from baseline to Week 48 in the LogMAR acuity will be the primary response. The change from baseline of all-GS010 eyes will be compared to the change from baseline of all-Sham eyes (intra-subject comparison) using a mixed model of analysis of covariance (ANCOVA) using the following terms (or covariate) in the model:

- Subject as random factor
- Eyes of the subject as random factor,
- Treatment and the
- Baseline LogMAR for each eye.

The analysis will be performed based on alpha of 0.05. The statistical significance in favor of GS010 against sham will provide evidence of the advantage of using GS010 for halting visual acuity loss or improving visual acuity in subjects with LHON with duration of vision loss of 6 months or less. The difference in the mean change from baseline (adjusted mean difference) to Week 48 between the two treatment groups and associated 95% confidence interval will be reported.

The center will not be included in the analysis as the number of subjects recruited per site will be very small. However, stratification by geographical area will be performed as a sensitivity analysis. Neighboring countries can be pooled together to reach at least 9 subjects per geographical entity. The pooling will be performed during the masked review of data.

All the model diagnostics will be checked.

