#### Sensitivity Analyses

The primary analysis with the same model will be repeated for the following lists.

- 1) Per protocol
- 2) Randomized subjects even if they were not treated and assigned treatment by randomization instead of actual treatment received
- 3) Secondary handling of missing data
- 4) Model with geographical area effect
- 5) Model excluding major outliers if any
- 6) Analysis of absolute Week 48 LogMAR values
- 7) Baseline GCL thickness/volume
- 8) Best or worst-seeing eye (eye status) added as a binary covariate
- 9) Duration of vision loss at the time of Screening added as a covariate in the model

All these analyses will be presented in a forest plot displaying treatment effect, 95% confidence intervals and p-value. The analysis will also be presented in tabular format.

- 10) Non-parametric Analysis: Wilcoxon signed-rank test will be performed as a sensitivity analysis to compare between all-GS010 eyes and all-Sham eyes
- 11) On-chart eyes at baseline
- 12) Off-chart eyes at baseline
- 13) Analysis of absolute Week 48 LogMAR values for on-chart eyes at baseline
- 14) On-chart eyes at baseline and per protocol population
- 15) On-chart eyes at baseline and all randomized subjects
- 16) On-chart eyes at baseline and Secondary handling of missing data
- 17) On-chart eyes at baseline and Duration of vision loss at the time of Screening added as a covariate in the model
- 18) On-Chart eyes at baseline and at Week48, Week 72 and Week 96
- 19) Off-Chart eyes at baseline and at Week48, Week 72 and Week 96

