#### Primary Analysis for FDA

The null and alternative hypotheses for the primary endpoint are defined below

$$H_0: \mu_{\text{best-GS010}} = \mu_{\text{best-Sham}}$$

$$H_1: \mu_{\text{best-GS010}} \neq \mu_{\text{best-Sham}}$$

Where  $\mu$  presents the mean change from baseline to Week 48 in LogMAR and “best” indicates best-seeing eyes.

The primary analysis will be performed on the ITT population. The change from baseline to Week 48 in the LogMAR acuity will be the primary response. The change from baseline of the best-GS010 eyes will be compared to the change from baseline of the best-Sham eyes (inter-subject comparison) using analysis of covariance (ANCOVA) including treatment as a main effect and baseline LogMAR as a covariate in the model. The analysis will be performed based on alpha of 0.05. The statistical significance in favor of Best-GS010 eyes against Best-sham eyes will show evidence of the advantage of using GS010 in the best eye for halting visual acuity loss or improving visual acuity in subjects with LHON with a duration of vision loss of 6 months or less. The difference in the mean change from baseline (adjusted mean difference) to Week 48 between the two treatment groups and associated 95% confidence interval will be reported.

The center will not be included in the analysis as the number of subjects recruited per site will be very small. However, stratification by geographical area will be performed as a sensitivity analysis. Neighboring regions will be pooled together to reach at least 9 subjects per geographical entity. The pooling will be performed during the masked review of data. An additional model will add the treatment by geographical area interaction to test for lack of generalizability of treatment effect.

The same analysis will be repeated for worst-GS010 eyes against worst-Sham eyes.

All the model diagnostics will be checked.

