#### Sensitivity Analysis

Primary analysis with the same model will be repeated for the following lists.

- 1) Per protocol
- 2) Randomized subjects including those not treated
- 3) Secondary handling of missing data
- 4) Model with country effect
- 5) Model excluding major outliers if any (defined as a standardized endpoint greater than the absolute value of 4.0)
- 6) Analysis of absolute Week 48, Week 72 and Week 96 LogMAR values, without covariate adjustment
- 7) Baseline GCL layer thickness/volume
- 8) Duration of vision loss at the time of treatment as a covariate

All these analyses will be presented in a forest plot displaying treatment effect, 95% confidence intervals and p-value.

- 10) Non-parametric Analysis: Wilcoxon Rank-Sum test will be performed as a sensitivity analysis to compare between Best-GS010 eyes and Best-Sham eyes.
- 11) On-chart eyes at baseline
- 12) Off-chart eyes at baseline
- 13) Analysis of absolute Week 48, Week 72 and Week 96 LogMAR values for on-chart eyes at baseline

- 14) On-chart eyes at baseline and per protocol population
- 15) On-chart eyes at baseline and all randomized subjects
- 16) On-chart eyes at baseline and Secondary handling of missing data
- 17) On-chart eyes at baseline and Duration of vision loss at the time of Screening added as a covariate in the model
- 18) On-Chart eyes at baseline and at Week48, Week 72 and Week 96
- 19) Off-Chart eyes at baseline and at Week48, Week 72 and Week 96

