#### Time Course of the response

Time course of response will be explored in two ways:

The ANCOVA model for primary end point comparing All-GS010 and All-Sham eyes will be used for each visit for the estimation of treatment effect. The treatment effect estimate of each visit will be multiplied by -50 to convert change LogMAR to change of ETDRS letters.

Treatment estimate (LS means difference between All-GS010 and All-Sham) and associated 95% confidence interval will be plotted for each visit.

Time course analysis will compare time course of the response up to Week 48 using the mixed model procedure. The change from baseline to Week 48 in the LogMAR will be the response. The change from baseline of all GS010 eyes will be compared to the change from baseline of all sham eyes using a mixed model of repeated measure (MMRM) including the subject and the eyes of the subject as random factors, the treatment, Visit, eye status at baseline (Best or worst), interaction between eye status at baseline and treatment, interaction between visit and treatment and baseline as covariates in the model. The estimate of treatment effect at various time points and its 95%CI (without adjustment for multiplicity) will be presented. Unstructured covariance structure will be fitted. In case of any convergence problem with this covariance structure other covariance structures like compound symmetry (CS) will be used.

Three graphical presentations will be performed:

- 1) A graph with the time course of the response for the treated best eye, the sham best eye, the treated worst eye and the untreated worst eye.
- 2) A graph with the time course of the response of the treated eye (irrespective of the status at baseline) and the sham eye (irrespective of the response).
- 3) A graph with the time course of the response of the treatment effect (delta between treatment groups) for the best Seeing Eye at baseline and for the worst Seeing Eye at baseline.

In the graphs the pertinent p values including that of interaction between eye status and treatment, time effect, treatment effect, treatment by time interaction will be displayed.

Two additional analyses with the same model (excluding eye status and treatment interaction) for the best-seeing Eye and for the worst-seeing will be performed (sub-group analysis).

The same analysis will be continued for up to Week 96-time course.

All the model diagnostics will be investigated.

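### SAP 5.7.1, secondary imputation Rule 2: the between-eye difference is scaled by a ratio whose denominator can be near zero, and no per-eye LogMAR is defined for the models that are rerun

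*SAP*

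**What the plan says.** SAP 5.7.1 gives a primary and a secondary imputation method for a missing Week 48 LogMAR. Rule 1, linear interpolation, is common to both. Rule 2 covers subjects who leave and have no later visit: "If there is no following visit due to drop out then the relative change" is computed and applied forward from the last available visit. In the primary method the relative change comes from sham eyes and is applied to each eye's own LogMAR. In the secondary method it is based on the between-eye difference, over subjects attending both visits: "RCi is then the relative change from visit i to visit i+1 of the difference between treated and sham eye".

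The secondary method is used in SAP 9.5.1, in item 3 of both sensitivity lists ("Secondary handling of missing data") and in item 16 of both ("On-chart eyes at baseline and Secondary handling of missing data"). Each list repeats its primary analysis with the same model. The EMA model is a mixed ANCOVA on both eyes, with a "Baseline LogMAR for each eye" term. The FDA model compares best-seeing eyes between subjects, "using analysis of covariance (ANCOVA) including treatment as a main effect and baseline LogMAR as a covariate in the model".

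Protocol 12.7 describes the same second method but pairs it with a one-sample t-test on the Week 48 between-eye difference. SAP 5.7.1 does not contain that sentence.

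**The concern.** There are two problems, both confined to Rule 2 of the secondary method.

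First, a relative change is only useful if its denominator is safely away from zero. Here the denominator is the treated-minus-sham difference. The treated eye is chosen at random and treatment is balanced over best-seeing eyes (SAP 3.4), so the mean difference is expected to be about zero at baseline. Under the null hypothesis it stays about zero at every visit. The SAP has no rule for a zero or sign-changing denominator. It also does not say whether the relative change is a ratio of means or a mean of subject ratios.

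Second, a projected difference does not determine either eye's value, yet the rerun models need one.

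At stake is whether a sensitivity analysis meant to test robustness to dropout can be run as written, and whether it responds to the data or to noise in a denominator.

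**Working it through.** **The plan's own figure.** SAP 3.3: n = 36, difference 0.3 LogMAR, SD of the between-eye difference in change 0.594, two-sided alpha 0.05. Standardised difference 0.3/0.594 = 0.505; noncentrality 0.505 × √36 = 3.03; paired t-test with 35 df gives 83.8%. The stated 84% is reproduced.

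**The multiplier.** Let D be treated minus sham LogMAR. RC = (D(i+1) - D(i)) / D(i), so the last difference is multiplied by 1 + RC = D(i+1)/D(i).
- Completer mean from -0.02 to -0.10: RC = -0.08/-0.02 = +4. A dropout at -0.30 becomes -0.30 × 5 = -1.50.
- Completer mean from +0.02 to -0.10: RC = -0.12/0.02 = -6. The same dropout becomes -0.30 × (-5) = +1.50.

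A 0.04 shift in a mean whose standard error is about 0.594/√36 = 0.099 moves the imputed value by 3 LogMAR.

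**Simulation.** Assumptions not in the documents: D is normal with SD 0.594 at each visit (the SAP gives this SD only for the Week 48 difference in change); visit-to-visit correlation is 0.6 to 0.8; RC is a ratio of completer means. The 5th to 95th percentiles of the multiplier, with two ranges given for correlations 0.6 and 0.8, are:

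| True D, last visit then Week 48 | Multiplier | Share negative |
|---|---|---|
| 0, 0 | -4.5 to 5.7; -3.0 to 4.6 | 30%; 21% |
| 0, -0.3 | about -23 to 25 | 50% |
| -0.15, -0.3 | -2.2 to 7.5; -1.7 to 6.7 | 6% |
| -0.25, -0.3 | 0.7 to 2.5; 0.8 to 2.1 | 0.6% |
| -0.3, -0.3 | 0.6 to 1.8; 0.7 to 1.5 | 0.2% |

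Power of the one-sample t-test on the Week 48 difference, true value -0.3, with 1 / 2 / 4 dropouts:

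| True D at last visit | Ratio rule | Additive rule |
|---|---|---|
| 0 | 57–59 / 46–47 / 33–34% | 83–84% |
| -0.15 | 76–78 / 72–74 / 66–68% | 83–84% |
| -0.25 | 83 / 82–83 / 80–82% | 83–84% |
| -0.3 | 83–84% throughout | 83–84% |

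The additive rule is D(i+1) = D(i) + mean completer change in D. Repeat runs agreed within about 1 to 1.5 points. Under the null with 1 to 4 dropouts, the ratio rule rejects in 4.3–5.2% of trials and the additive rule in about 5–6%.

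If RC were instead a mean of subject ratios, it would be unstable even with an established effect. With a mean of -0.30 at both visits (correlation 0.7, 35 completers), the 95% range of the multiplier is -7.3 to 8.7. It is undefined for any subject with equal eyes at visit i, and SAP 3.4 foresees ties in acuity.

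**Per-eye value.** A projected difference of -0.30 fits treated/sham pairs 0.5/0.8, 0.9/1.2 and 1.3/1.6 equally well. Neither the two-eye model nor the best-seeing-eye ANCOVA has a defined response for such a subject.

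**The case against.** The strongest case concerns weight. SAP 9.5.3 makes every analysis other than the primary one supportive. The rule applies only to a subject with neither a Week 48 value nor a later visit. Protocol 6.2 asks withdrawals to complete an end-of-study visit and seeks Week 48 acuity where possible. No dropout rate is stated. The largest losses need no effect at the last visit and the full effect at Week 48; the last visit could be as late as Week 24, and the documents give no trajectory. All of this stands, and it limits the severity.

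It can also be said that Protocol 12.7 still specifies the t-test, which needs no per-eye value, and that SAP silence does not clearly revoke it. That would settle the paired comparison, but not the best-seeing-eye ANCOVA, and the SAP's instruction to rerun the same model conflicts with it.

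A reader might infer that the per-eye step would have to be invented after unmasking. The documents do not support that: it could be set in the programs, which Appendix V of the protocol wants validated before the first masked data review. It would, however, be a choice the SAP does not record.

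A reader might also infer that dropout is examined in no other way. That is not so. The time-course analysis fits all visits "using a mixed model of repeated measure (MMRM) including the subject and the eyes of the subject as random factors", with no ratio imputation specified, and the per-protocol set requires a completed Week 48 assessment.

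**Conclusion.** Both points hold on the text. As written, the secondary Rule 2 can produce imputed differences of arbitrary size and sign when the between-eye difference at the last visit is small, and it does not define the response for the models that items 3 and 16 rerun.

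The size is illustrative. With one dropout it runs from about 58% against 84% power when there is no effect at the last visit, through 76–78% at -0.15 and about 83% at -0.25, to no loss at -0.3. These figures rest on the assumed SD at each visit, the visit correlation, ratio-of-means averaging and the assumed trajectory.

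Two stronger readings are not supported. The ratio rule does not inflate type I error: its null rejection is at or near 5%. Nor does the point reach the primary result, because the primary method scales each eye's own LogMAR and does not divide by a between-eye difference. Severity is low, but the wording is worth correcting while that is still possible.

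**What to change.** Before the code break, since Appendix V of the protocol bars SAP amendments afterwards:

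1. Replace the secondary Rule 2 with an additive one: D(i+1) = D(i) + mean change in the between-eye difference among subjects attending both visits. This also settles how the change is averaged.
2. State the per-eye step for items 3 and 16 of both lists: impute the sham eye by the primary rule and set the treated eye to sham eye + D. Restore the one-sample t-test of Protocol 12.7 for the paired comparison.
3. Align Protocol 12.7 with SAP 5.7.1. Protocol 12.1 leaves data handling detail to the SAP, but an additive rule replaces one the protocol states, and Protocol 15 requires an amendment with IRB/IEC approval for a permanent change.

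Two downsides should be stated in the SAP. Additive single imputation is slightly anti-conservative: about 5–6% null rejection for the t-test with 1 to 4 dropouts, and 5.2–7.0% in a simulation of the mixed model (assumed between-eye correlation of change 0.5; pair mean LogMAR 1.3, 1.4 and 1.5 at baseline, last visit and Week 48; 18/18 balance of best-seeing eyes). In the best-seeing-eye ANCOVA, a dropout whose best eye received sham keeps its primary imputation, so only dropouts whose best eye received GS010 change.

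The cost is a few lines in the SAP and a matching protocol amendment. There is no data or patient cost.
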